6.7 BASELINE, TIME WINDOWS AND CALCULATED VISITS

Study days and visits will be labelled according to the flow chart of the CTP.

Unless otherwise specified, baseline is defined as the time-point closest to but prior to first administration of study medication. If no time is specified and the date is the same as the first administration date, then it will still be considered baseline if not specified otherwise.

Laboratory values: Baseline is defined as the latest time-point before start of the very first administration of study medication. For laboratories where not only the examination date but also time are recorded, examination time has to be taken into account when defining baseline. That is, a laboratory value on the same date as the first study drug administration is considered as baseline value if and only if the time of laboratory value is before or the same as the time of the start of first study drug administration.

If any of these times are missing (either no time of start of first study drug administration or no lab sample stating that it was taken prior to start of first study drug administration) and so it cannot be concluded whether the blood sampling was done before or at the same time of the start of first study drug administration, the last available laboratory assessment before first study drug administration will be taken (Screening laboratory).

For graphical presentations of laboratory data, baseline will be coded as Day = 1.

7. PLANNED ANALYSIS

For End-Of-Text tables, the set of summary statistics is: N / Mean / standard deviation [StD] / Min / Median / Max. Efficacy data are presented by dose cohort. Displays of safety data will be presented by dose cohort and in total.

For tables that are provided for endpoints with some extreme data, median, quartiles and percentiles should be preferred to mean, StD, min and max.

For time-to-event analysis tables, the set of statistics is: number of patients [N(%)], Number of patients with event [N(%)], <Time to event> [months] followed by P25 (25th percentile), median, P75 (75th percentile), Number of patients censored [N(%)]. If not specified otherwise, the duration as well as the time to event will be displayed in months and a final decision will be made at the last BRPM.

Tabulations of frequencies for categorical data will include all possible categories and will display the number of observations in a category as well as the percentage (%) relative to the respective treatment group (unless otherwise specified, all patients in the respective patient set whether they have non-missing values or not). Percentages will be rounded to one decimal place. The category missing will be displayed only if there are actually missing values. The denominator of the main categories is defined by the number of patients in the used patient set. The main categories define the denominators of the subcategories. Subcategories should be intended and "[N(%)]" will be displayed only for the main category. If a table includes only categorical data, "[N(%)]" is to be displayed in the column header.

If applicable, conversion from days to weeks, months and years will be as follows:

- Weeks = Days/7
- Months = $(Days \times 12)/365.25$
- Years = Days/365.25

7.1 DEMOGRAPHIC AND OTHER BASELINE CHARACTERISTICS

7.1.1 Disposition of patients

For patient disposition the standard descriptive table will be populated. Additionally, patients with discontinuations by initial treatment and the reasons will be listed. An overview table with respect to analysis sets (as defined in Section 6.3) together with the primary reason for exclusion will be provided.

7.1.2 Important protocol violations

A listing with protocol violations by patient will be created in Section 15 of the CTR.

7.1.3 Demographic and other baseline characteristics

Standard descriptive analysis and summary tables for all patients treated by initial treatment will be created for demography, alcohol status, ECOG performance score, previous therapies, baseline values of haemoglobin, neutrophil, platelet, lymphocyte count, tumour size, virology and oncology history.

7.2 CONCOMITANT DISEASES AND MEDICATION

Only descriptive statistics are planned for this section of the report.

Concomitant therapies (CTh) will be coded according to World Health Organisation Drug Dictionary (WHO DD). They will be classified according to the Anatomical, Therapeutic, Chemical (ATC) classification system. The third ATC level will be used to categorise CThs by therapy type. In situations where a medical product may be used for more than one equally important indication, there are often several classification alternatives. As appropriate, patients receiving CThs with more than one possible ATC level-three category will be counted more than once; footnotes will clarify this possible double counting in tables.

Summaries will be presented for previous and concomitant medications started at baseline and for concomitant therapies started after first administration of the trial medication. Separate summaries will be presented for concomitant medications with missing or incomplete start dates.

Listings of the data will present the concomitant therapy PT and verbatim text as well as the verbatim text of the indication. In addition the listings will include study day for start and stop dates and duration of therapy. Patients with no concomitant therapy will not be included in the listing. A separate listing will be provided for patients receiving Granulocyte-Colony Stimulating Factor (G-CSF) and transfusions (ATC Codes L03AA, B05AA, B05AX).

7.3 TREATMENT COMPLIANCE

Compliance will be evaluated by whether or not the medication was always administered according to protocol for BI 836826.

A listing will show all administrations of trial drug including the comment if administration was not according to protocol and also the administration of premedication acetaminophen/paracetamol, antihistamine and glucocorticoid will be included.

7.4 PRIMARY ENDPOINT(S)

The primary endpoints of this trial are the MTD and the number of patients with DLTs during the MTD evaluation period. The MTD is determined from the occurrences of DLTs during the MTD evaluation period, i.e. the number of patients with DLTs during the first course. An overall summary of the DLTs (see CTP Section 5.2.1.1 for definitions of DLT) which occurred during the MTD evaluation period will be provided for each dose cohort of the MTD evaluation set. Patients, if any, who did not complete the first treatment course with BI 836826 for reasons other than DLT will be excluded from the analysis of the primary

endpoint, since they are by definition not part of the MTD evaluation set. These patients were replaced at the same dose level. A summary of the number of patients with DLTs overall in any course will be also given by initial treatment and displayed in a similar format to the summary of DLTs occurring in the MTD evaluation period.

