#### **3.3.4** Removal of patients from therapy or assessments

#### 3.3.4.1 Removal of individual patients

An individual patient is to be withdrawn from the trial if:

- The patient withdraws consent. Patients are free to discontinue their participation in this trial at any time without the need to justify the decision.
- The patient needs concomitant drugs which may interfere with the investigational product (please refer to Section 4.2.2).
- The patient is no longer able to participate for other medical reasons (e.g. adverse events unrelated to therapy or disease progression, concomitant diagnoses, pregnancy, surgery or administrative reasons). The investigator may also stop a patient's participation if the patient is no longer able to attend trial visits.

A patient can be withdrawn after discussion between the investigator and the Clinical Monitor at Boehringer Ingelheim if eligibility criteria are violated and/or the patient fails to comply with the protocol.

All withdrawals will be documented and the reason for withdrawal recorded and discussed, as necessary, in the final report of the trial. As soon as a patient is withdrawn from the trial, the next scheduled visit and the EOT have to be performed if feasible. Every effort should be made to follow-up patients in case an AE is still ongoing at the time of withdrawal.

A patient has to discontinue trial drug administration in case

- A DLT occurs which does not recover to a degree that allows treatment continuation.
- PD or any other concomitant diagnosis/symptom develops resulting in an indication to start any other therapy for CLL, including deterioration of general condition.

Patients who have not completed at least one course will be replaced. Patients who terminate trial treatment due to DLT will not be replaced.

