Administration of the trial drug has to be stopped temporarily in case of a DLT (see Section 5.2.1.1). Patients may continue therapy only after recovery from the DLT to at least CTCAE grade 1 or pre-treatment value. The future dose of BI 836826 must be finally agreed on between the sponsor and the investigator. A reduction of the dose will be allowed only once for an individual patient during the whole trial. Treatment has to be discontinued in case the DLT is not reversible.

Intra-patient dose escalation may be considered in agreement between investigator and sponsor for selected patients. It is restricted to patients who have received at least 4 treatment courses and tolerate the treatment well at the time of dose escalation. Intra-patient dose escalation can only be performed at a time when the next higher dose cohort has been reviewed and considered safe by the DSMB. The dose escalation step is limited the dose which has been administered to the next higher cohort. The treatment courses at the increased dose have to follow the instructions as outlined for course 5-8 in the Flow Chart and the protocol. In addition, after the first dose at the higher dose level, patients have to be monitored for at least 24 hours after the end of the infusion, including safety laboratory for tumour lysis syndrome.

A log of all patients enrolled into the study (i.e. having given informed consent) will be maintained in the ISF at the investigational site irrespective of whether they have been treated with investigational drug or not.

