6.3 PATIENT SETS ANALYSED

The Screened Set (SCR) includes all patients who signed the informed consent form and will be used to summarize patient disposition.

^[2] IPV will be identified via individual review at MQRM/BRPM/DBL

The Treated Set (TS): consists of all patients who received at least one application of the BI drug BI 836826. The TS will be used for all planned safety and efficacy analyses.

The MTD evaluation set: This patient set includes all patients who were documented to have received at least one dose of study medication and were not replaced for the MTD evaluation. The MTD evaluation set will be used for the primary analyses of DLTs and MTD determination.

Rules for replacement of patients are defined in Section 3.3.4.1 of the CTP. The list of replaced patients will be provided by the Trial Clinical Monitor no later than the last BRPM and should be attached to the BRPM minutes.

No per protocol population will be used for analyses.

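### Replacement and membership of the MTD evaluation set depend on the recorded reason for leaving course 1, so a first-course DLT can fall out of the primary DLT count

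*SAP*

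**What the plan says.** Three rules decide who enters the primary analysis.

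- **Protocol 3.3.4.1** (removal of individual patients): "Patients who have not completed at least one course will be replaced". The one exception is "Patients who terminate trial treatment due to DLT will not be replaced".
- **SAP 6.3** (patient sets): the MTD evaluation set holds patients who "received at least one dose of study medication and were not replaced for the MTD evaluation". It refers to protocol 3.3.4.1 for the replacement rules and adds that "The list of replaced patients will be provided by the Trial Clinical Monitor no later than the last BRPM". On use: "The MTD evaluation set will be used for the primary analyses of DLTs and MTD determination".
- **SAP 7.4** (primary endpoints): for the primary endpoint, patients "who did not complete the first treatment course with BI 836826 for reasons other than DLT will be excluded from the analysis of the primary" (the sentence is cut short here), on the ground that they are outside the MTD evaluation set by definition.

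Two other places define the quantity being estimated. Protocol 3.1 counts the patients at a dose level who experience a DLT and treats two or more among up to six as exceeding the MTD. SAP 5.1 takes the MTD as the highest dose studied with a DLT incidence of at most 17% (1/6) in the MTD evaluation period, which is the 14 days after first administration. Neither attaches a condition on why a patient left.

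**The concern.** The exception in protocol 3.3.4.1 and the exclusion in SAP 7.4 cover the same ground only if every course 1 DLT in a non-completer is also the recorded reason for stopping. The protocol does not ensure this. Under section 4.1.4, "Administration of the trial drug has to be stopped temporarily in case of a DLT", and permanent discontinuation follows only if the DLT does not reverse. Section 3.3.4.1 lists other exits that may apply meanwhile: withdrawal of consent without justification, progression leading to other CLL therapy, other medical reasons, and withdrawal for an eligibility violation after discussion with the sponsor.

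A patient with a course 1 DLT who takes one of these exits before completing the course meets the wording for replacement and exclusion. No sentence in either document says that a patient with a course 1 DLT is always evaluable. What is at stake is the primary endpoint itself, in cohorts of three to six where one patient can decide the result.

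**Working it through.** **The plan's own figures.** The 17% limit is 1/6 = 16.7%. The escalation sample size reproduces: 3×1 + 3×3 + 3×6 = 30, and 30 + 30 for the expansion cohort = 60. This point changes none of these.

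**The rules side by side, for one patient** (course 1 DLT, course not completed, recorded reason is withdrawn consent):

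| Source | Test applied | Result |
|---|---|---|
| Protocol 3.1 | Experienced a DLT at this dose level? | Counted |
| SAP 5.1 | DLT in the MTD evaluation period? | Counted |
| Protocol 3.3.4.1 | Stopped treatment because of DLT? | No, so replaced |
| SAP 6.3 | Dosed and not replaced? | No, so outside the set |
| SAP 7.4 | Non-completion for a reason other than DLT? | Yes, so excluded |
| SAP 7.8.1.1, treated-set table | Treated, with a DLT in course 1? | Shown |

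**Worked count.** Seven patients are dosed at one level and two have a course 1 DLT. One of the two leaves early for another recorded reason and is replaced by a patient without a DLT.

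- Current wording: the MTD evaluation set shows 1/6 = 16.7%, within the limit.
- Treated set: 2/7 = 28.6%.
- If the patient with the DLT is kept and not replaced: 2/6 = 33.3%, and the MTD is exceeded under protocol 3.1.

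**Direction.** A dropped patient contributed one DLT; the replacement contributes none or one. The count in the set can therefore equal or fall below the count with the patient kept, and never exceed it.

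**Conditional effect on escalation.** This applies only if cohort decisions use the replacement rule. Let p be the true DLT rate and f the share of DLT patients lost in this way. The documents give neither, so both are assumptions. Patients without a DLT are assumed to complete course 1.

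- DLT rate among retained patients: p′ = p(1 − f)/(1 − pf).
- Escalation follows 0/3, or 1/3 and then 0/3: P = (1 − p′)³ + 3p′(1 − p′)² × (1 − p′)³.

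For p = 1/3 and f = 0: (2/3)³ = 0.296 and 3(1/3)(2/3)² = 0.444, so P = 0.296 + 0.444 × 0.296 = 0.428.

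| f | p′ (p = 1/3) | P(escalate) |
|---|---|---|
| 0 | 0.333 | 42.8% |
| 10% | 0.300/0.967 = 0.310 | 47.3% |
| 20% | 0.267/0.933 = 0.286 | 52.4% |
| 30% | 0.233/0.900 = 0.259 | 58.0% |

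At p = 0.25 and f = 20%, p′ = 0.200/0.950 = 0.211 and P rises from 60.0% to 68.6%. For p from 0.17 to 0.50 the rise is about 1.5 to 4.5 points at f = 5–10%, and at most about 15 points at f = 30%.

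The no-dropout assumption matters. If patients without a DLT also left course 1 at rate f and were replaced, then p′ = p(1 − f)/[p(1 − f) + (1 − p)(1 − f)] = p, and the rate would not be biased on average. The observed DLT would still be missing from the count.

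**The case against.** The strongest reply is that escalation is not run from the SAP's analysis set. Protocol 3.1 counts patients who experience a DLT. Under section 4.1.3, data from all previous cohorts go to the coordinating investigator, the sponsor and the DSMB before each step, and section 5.2.1.1 sends all DLT-qualifying events to the DSMB. SAP 7.8 describes its MTD tables as documenting the data behind a selection already made. This stands. A reader might infer that the SAP wording itself makes over-escalation more likely; the documents do not support that, and the probabilities above are conditional.

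Further replies carry weight.

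- **DLTs considered elsewhere.** Protocol 5.2.1.1 says that for patients given more than one dose, all events meeting the DLT definition are considered in confirming the MTD. Course 1 normally has two doses, so the literal text could cover this patient, although it may be aimed at later courses. Protocol 7.3.1 asks for the number of DLTs at each dose level without an exclusion. Neither changes the SAP's definition of the primary set.
- **Few patients qualify.** Course 1 drug is normally all given by day 2 (protocol 4.1), and neither document defines completion of a course. If completion means dosing, a patient with a DLT on day 5 who leaves on day 10 has completed the course and is counted. If it means 14 days, the patient is not. A DLT that does not recover also requires discontinuation, so DLT will often be the recorded reason.
- **The monitor's list.** A reader might infer that membership is chosen late with outcomes known. SAP 6.3 ties replacement to protocol 3.3.4.1, and replacements are enrolled at the same dose level; nothing says the list decides them afterwards.
- **Visibility.** SAP 7.8.1.1 tabulates course 1 DLTs for both sets, so a dropped DLT would appear as a difference between them.

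These replies limit the consequence. They do not remove the conflict between the definitions.

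**Conclusion.** The point holds at moderate severity. Protocol 3.3.4.1 and SAP 6.3 and 7.4 select patients by reason for leaving, while protocol 3.1 and SAP 5.1 define the MTD by occurrence of a DLT, and the two disagree for a patient with a DLT who leaves course 1 for another recorded reason. The certain effect, should such a patient occur, is that the primary DLT count and the documented basis for the MTD omit an observed DLT. One such patient can turn 2/6 into 1/6, or 1/3 into 0/3, provided the replacement has no DLT.

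The rise in escalation probability from 43% to 47–58% rests on three assumptions: a true rate of 1/3, 10–30% of DLT patients lost with no early leaving among the others, and cohort decisions that follow the replacement rule. It is not a finding about how this trial escalates. The situation is probably uncommon, and the event stays visible in the treated-set table and to the DSMB.

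**What to change.** Reconcile protocol 3.3.4.1 with SAP 6.3 and 7.4 by stating that:

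1. any treated patient with a DLT in the MTD evaluation period is evaluable, is not replaced and is counted, whatever the recorded reason for leaving;
2. only patients without a DLT who did not complete course 1 are replaced and excluded, with completion defined against the 14-day MTD evaluation period;
3. the MTD evaluation set is derived from the DLT and course 1 completion data, with the clinical monitor's list as a cross-check.

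The cost is a few sentences across the two documents. No new data are needed and the planned 30 and 60 patients stand. The DLT rate at a dose may look slightly less favourable, because patients with a DLT who leave early are kept while those without one are still replaced.

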7.5 SECONDARY ENDPOINTS

7.5.1 Key secondary endpoints

Not applicable.

7.5.2 Secondary endpoints

Number of lymphocytes in the peripheral blood

The number of lymphocytes in the peripheral blood will be analyzed in terms of the best percentage change from baseline until start of subsequent CLL therapy or PD. Best percent change is thereby derived by taking the difference between the baseline value and the minimum of all observed values over time. For the primary analysis of this endpoint, summary statistics will be presented for all patients of the TS by dose cohort and in total. In addition, summary statistics will be presented separately for patients of the TS with an abnormal and normal lymphocyte count at baseline. An abnormal baseline count is defined as a lymphocyte count $> 4*10^9$ /L. In addition, the following will be analysed:

Summary statistics will additionally be presented for minimum values of certain lymphocyte types (CD19+ B-cells, CD3+ T-cells, CD4+ T-cells, CD8+ T-cells and CD56+ NK-cells).

For CD4+ T-cells and CD19+ B-cells, the lowest count since start of treatment (nadir) and the time point of occurrence of (nadir) will be derived and described by summary statistics for all dose cohort together and separated by dose cohort. The association of values at baseline and values at nadir will be displayed graphically.

A waterfall plot will also be generated to summarise reduction of lymphocytes graphically and lymphocyte values will be graphically displayed over time for patients of the Treated Set. Furthermore, the number of lymphocytes and the change in lymphocyte count from baseline will be listed by time point.

Blood counts (haemoglobin, platelets, neutrophils)

[figure not shown]
A frequency table will be given for the endpoints "Number of patients with improved haemoglobin / platelet / neutrophil count for at least 2 subsequent response assessments" for all patients of the Treated Set. Additionally, graphical presentations of mean values of haemoglobin, platelet and neutrophil counts over time will be provided by dose cohorts. For neutrophils, the nadir and the time point of occurrence of nadir will be derived and described by summary statistics for all dose groups together and separated by dose group. The association of values at baseline and at time to nadir will be displayed graphically.

[figure not shown]
Best overall response

Best overall response will be analysed descriptively. Frequency distributions will be used to examine this endpoint. The number of patients that have either CR, CRi or PR as best overall response will be tabulated separately (to determine the remission rate).

Progression-free and Failure-free survival

PFS and FFS will be analysed exploratory using Kaplan-Meier methods for all patients of the Treated Set.

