#### 7.3.2 Secondary analyses

#### 7.3.2.1 Number of lymphocytes in the peripheral blood

The number and the change of lymphocytes in the peripheral blood will be analysed descriptively by time point. The maximal reduction of lymphocytes with respect to all time points after baseline will be analysed.

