4. CHANGES IN THE PLANNED ANALYSIS OF THE STUDY

4.1 CLARIFICATIONS

As this trial is the first in human use of BI 836826, the primary objective as defined by the Clinical Trial Protocol (CTP) is to determine the maximum tolerated dose (MTD) of BI 836826. The MTD is determined via the number of dose limiting toxicities (DLTs). The CTP does not contain any definition of primary endpoint. But to follow the definition of the primary objective of the trial as defined by the CTP, the MTD and the number of patients with DLTs during the MTD evaluation period are defined as primary endpoints (see Section 5.1).

During the course of the trial it was decided to change the definition of some of the secondary and further endpoints:

1. Number of lymphocytes in the peripheral blood

The definition of this endpoint was changed from "Number of lymphocytes in the peripheral blood" to "Best % change from baseline in number of lymphocytes in the peripheral blood".

2. Blood counts (haemoglobin, platelets, neutrophils, red blood cells)

The definition of this endpoint was changed from "Blood counts (haemoglobin, platelets, neutrophils, red blood cells)" to "number of patients with improved haemoglobin count for at least two subsequent response assessments", "number of patients with improved platelet count for at least two subsequent response assessments" and "number of patients with improved neutrophil count for at least two subsequent response assessments". It was decided to abandon the definition of a separate secondary endpoint for red blood cells, since red blood cells are highly correlated with haemoglobin count and are thus reflected in this endpoint.

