5.2.2 Other Secondary endpoints

Note: For the response/efficacy analyses with respect to overall response assessment by investigator used: If patients would have their examinations contributing to the disease assessment over a number of days, the earliest date of the multiple examinations should be considered.

For the response/efficacy analyses with respect to lymphocytes and blood counts only laboratory data assessed >= 8 days after the last infusion and with reported laboratory response assessment on-treatment and before start of new Chronic Lymphocytic Leukaemia (CLL) therapy is used. The reason for this approach is that otherwise the respective values of lymphocytes and blood counts would be biased due to the infusion after which an immediate change in values of the respective blood parameters is observed. This change though does not reflect an efficacy effect.

Number of lymphocytes in the peripheral blood

The secondary endpoint with respect to number of lymphocytes in the peripheral blood is defined as "Best % change from baseline in number of lymphocytes in the peripheral blood".

Blood counts (haemoglobin, platelets, neutrophils)

The secondary endpoints with respect to blood counts are defined as

- "Number of patients with improved haemoglobin count for at least two subsequent response assessments"
- "Number of patients with improved platelet count for at least two subsequent response assessments"
- "Number of patients with improved neutrophil count for at least two subsequent response assessments"

An improvement is indicated by the fulfilment of the criteria for "Complete Remission" or "Partial Remission", i.e.

- Haemoglobin count: Greater than 11g/dL or increase of 50% or more compared to baseline if haemoglobin is less than or equal to 11g/dL
- Platelet count: Greater than 100 000/ μ L or increase of 50% or more compared to baseline if platelets are less than or equal to 100 000/ μ L
- Neutrophil count: Greater than 1500/ μL or increase of more than 50% compared to baseline if neutrophil count is less than or equal to $1500/\mu L$

Best overall response:

Response will be assessed according to the NCIWG guidelines (R10-4429) based on laboratory data from the peripheral blood and clinical examination by the investigator. Each patient will be assigned to one of the following categories:

- complete remission (CR)
- complete remission with incomplete marrow recovery (CRi)
- partial remission (PR)
- stable disease (SD)

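### SAP 7.5.2 summarises the lymphocyte endpoint by dose cohort only as a best-ever change, a minimum over a patient-specific number of assessments, and reduces the protocol's by-time-point analysis to a listing and plots

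*SAP*

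**What the plan says.** Protocol 7.3.2.1 plans two things. First: "The number and the change of lymphocytes in the peripheral blood will be analysed descriptively by time point". Second: "The maximal reduction of lymphocytes with respect to all time points after baseline will be analysed".

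SAP 4.1 declares a change of endpoint to "Best % change from baseline in number of lymphocytes in the peripheral blood". It gives no reason for this item, although it does give one for dropping red blood cells. SAP 7.5.2 analyses the "best percentage change from baseline until start of subsequent CLL therapy or PD", derives it from "the difference between the baseline value and the minimum of all observed values over time", and for the primary analysis of the endpoint "summary statistics will be presented for all patients of the TS by dose cohort and in total". A waterfall plot and a plot of counts over time are added. For the by-time-point analysis, "the number of lymphocytes and the change in lymphocyte count from baseline will be listed by time point".

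SAP 5.2.2 restricts the values that may enter: only "laboratory data assessed >= 8 days after the last infusion and with reported laboratory response assessment on-treatment", and before any new CLL therapy. Response is assessed once per course, before the next dose (Protocol 5.1.2.4 and flow chart), so this gives about one eligible value per course.

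Protocol 3.1 and 4.1.4 allow up to 4 courses in escalation, extended to 8 with clinical benefit, and up to 8 in the expansion cohort. Treatment beyond 8 courses is possible case by case.

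**The concern.** The minimum of several later values, set against a single baseline value, is an extreme-value statistic. Random variation alone pushes it below baseline, and more values push it further. The number of values is not fixed. It depends on early stopping, on judged benefit and on the phase of the trial, all of which can go with dose and outcome. A cohort whose patients stay longer can therefore show a deeper best change at the same true effect, and a cohort that loses patients early can look worse for that reason alone.

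Lymphocyte change by dose bears on the objectives: Protocol 2.2 names a relevant B-cell reduction as an example of evidence for an optimal biological dose, and Protocol 5.1.2.1 notes that in most of these patients malignant B-cells make up most of the blood lymphocytes. The planned analysis without this bias, change at a given time point, is the one that lost its summary.

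A second problem concerns dose attribution. Protocol 4.1.4 allows intra-patient dose escalation after at least 4 courses, while SAP 6.1 analyses patients under their initial dose. SAP 7.5.2 sets no cut-off at that escalation, so a minimum reached on a higher dose can be credited to a lower cohort.

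**Working it through.** **The plan's own figures.** None is given for this endpoint. The sample size in Protocol 7.6 reproduces: 3×1 + 3×3 + 3×6 = 30, plus 30 = 60. It shows that escalation cohorts have 1, 3 or 6 patients, so one or two early stoppers can move a cohort summary.

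**Inputs.** k eligible values per patient, one per 14-day course (SAP 5.2.2, flow chart): k = 1 after early stopping, 4 at the escalation limit, 8 in expansion or with extension. Follow-up for the minimum ends at progression (SAP 7.5.2), which includes a lymphocyte rise of 50% or more (Protocol 5.1.2.4.4; its further condition on the absolute B-lymphocyte count is not modelled). Two growth rates come from inclusion criterion 3(4): doubling in 6 months, and +50% in 2 months. The within-patient SD of the log count is not in the documents; 0.2 and 0.3 are assumed (CV of about 20% and 30%).

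**Formula.** Best change = 100 × (min(Y1,…,Yk) − Y0) / Y0. With no effect, no trend and no stopping, Y0,…,Yk are exchangeable, so P(best change < 0) = k/(k+1): 1/2 = 50%, 4/5 = 80% and 8/9 = 89% for k = 1, 4 and 8.

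**Simulation.** No drug effect, log-normal values, 200,000 patients per scenario, stopping at the first rise of 50% or more (that value counts as the last). Cells show the median best change and the share of patients below baseline.

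| Untreated course | SD | k = 1 | k = 4 | k = 8 |
|---|---|---|---|---|
| Stable | 0.2 | 0.1%; 50% | -17.9%; 76% | -23.6%; 80% |
| Stable | 0.3 | 0.1%; 50% | -23.5%; 70% | -29.4%; 71% |
| Doubling in 6 months | 0.2 | +5.4%; 43% | -6.9%; 60% | -8.0%; 62% |
| Doubling in 6 months | 0.3 | +5.2%; 45% | -12.6%; 61% | -14.0%; 62% |
| +50% in 2 months | 0.2 | +9.8%; 37% | +0.5%; 49% | +0.3%; 50% |
| +50% in 2 months | 0.3 | +9.8%; 41% | -4.7%; 54% | -5.1%; 54% |

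**Shift in the median at SD 0.2.**
- From k = 4 to 8: 23.6 − 17.9 = 5.7 points (stable), 8.0 − 6.9 = 1.1 (doubling).
- From k = 1 to 4: 0.1 + 17.9 = 18.0 points (stable), 5.4 + 6.9 = 12.3 (doubling).

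**Against the trial's 50% benchmarks** (Protocol 3.1 for B-lymphocytes; PR criterion A1). With stable counts and no effect, a best change of -50% or lower occurs in 2.5% (k = 4) and 4.1% (k = 8) of patients at SD 0.2, and in 14.4% and 21.0% at SD 0.3. A true reduction of 60% reads as about 67% at k = 4 and 70% at k = 8 (SD 0.2).

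**Fixed time point.** With stable counts and no effect, the median change is 0% and half the patients are below baseline, however many courses are given.

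**Timing under the 8-day rule.** At day 15, a patient dosed on days 1 and 2 is 15 − 2 = 13 days past infusion and eligible. A patient dosed on days 1, 2 and 8 (Protocol 4.1 and Appendix 10.6) is 15 − 8 = 7 days past infusion and not eligible, unless course 2 is delayed.

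**The case against.** Three stronger readings are tempting, and the documents do not support them.

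- **That the SAP replaced the protocol analysis.** Maximal reduction was already planned, SAP 4.1 declares the change, and by-time-point data remain as a listing and plots. SAP 7.8.2 also tabulates the last value and its difference from baseline for laboratory parameters, and plots absolute lymphocyte counts over time by cohort. This stands. However, the last value also falls at a patient-specific time, so it does not supply the missing summary.
- **That most patients show a reduction without drug effect, and more so with more courses.** This needs stable counts. Under doubling in 6 months the share is about 60% at both k = 4 and k = 8; under +50% in 2 months it is about half.
- **That cohorts cannot be compared fairly.** All escalation cohorts share the 4-course limit, and 8 courses there require clinical benefit, so 4 versus 8 mainly separates escalation from expansion. No formal test is planned (Protocol 7.2), and the expansion dose is agreed during the trial with DSMB review (Protocol 3.1), not read from this table. This stands for the limit itself, but not for early stopping, which can differ between neighbouring doses and gives the larger shift.

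Nor can this be called the main pharmacodynamic read-out: it is one of several secondary endpoints, SAP 7.5.2 also describes CD19+ B-cell nadirs by cohort, and parts of the pharmacodynamic sections are not public.

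**Conclusion.** The point holds in a limited form. One of two planned analyses was promoted to the only efficacy summary of lymphocyte change by dose cohort, and the other lost its summary statistics. The promoted statistic is biased towards a reduction, and comparison of cohorts is confounded by the number of assessments. For stable counts the bias is about 18 to 24 points in the median at 4 to 8 assessments with a CV of about 20%, and 23 to 29 points with about 30%. Under doubling in 6 months, the difference between 4 and 8 assessments nearly vanishes, while that between 1 and 4 stays at about 12 points at a CV of about 20%. These figures rest on the assumed CVs and on one eligible value per course. Beside a true reduction well above 50% the bias is small; it matters mainly at low doses and in cohorts that lose patients early. The possible crediting of a later, higher-dose minimum to the initial cohort is a separate gap and needs no such assumption.

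**What to change.** In SAP 5.2.2 and 7.5.2, add the Protocol 7.3.2.1 analysis as a summary table by dose cohort: percent change from baseline at the end of course 1 and of each later course, with n. Keep best percent change and the waterfall plot beside it, and report the number of eligible post-baseline values per patient.

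Three points need a sentence each:
- How the end-of-course-1 value is handled for patients dosed on days 1, 2 and 8, who fail the 8-day rule at day 15. They could be flagged or shown separately.
- That later-course rows include only patients who continued.
- Whether values after intra-patient dose escalation count towards the minimum. Rows up to course 4 are not affected, because escalation requires at least 4 courses.

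The cost is SAP wording and one table from data already collected. The end-of-course figures will look less favourable than the best-ever change and show later, deeper responses only in the later rows; the best-change summary still shows those.
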